10.4.6. Progression-Free Survival (PFS)

Progression-free survival (PFS) is defined as the time from the first dose date of study treatment until disease progression (per IWCLL 2008 criteria) or death from any cause, whichever occurs first.

In the MRD cohort and the Fixed Duration cohort, PFS is a secondary endpoint and will be analyzed in the all treated population. Distribution of PFS will be estimated using Kaplan-Meier method. Median PFS, landmark estimates, and their corresponding 95% CI will be provided.

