10.4.7. Overall Survival (OS)

Overall survival (OS) is defined as the time from the first dose date of study treatment until date of death due to any cause.

In the MRD cohort, and the Fixed Duration cohort, OS is a secondary endpoint and will be analyzed in the all treated population. Distribution of OS will be estimated using Kaplan-Meier method. Median OS, landmark estimates and their corresponding 95% CI will be provided.

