#### 4. ANALYSIS FOR ENDPOINTS

All endpoints will be analyzed in both MRD and FD cohorts separately and pooled except DFS for MRD cohort only. The definition and analysis methods are the same for both cohorts on the same endpoint with some variations on analysis population and analysis period in terms of primary analysis vs supportive analysis of the endpoint.

In general, the analysis population for the primary analysis is the all treated population for the MRD cohort and the non-del17p population for FD cohort. All analyses for the FD cohort will be repeated on the all treated population as supportive analyses.

Unless otherwise specified, the analysis period for primary analysis of endpoints is from the first dose date of study treatment to the first dose date of subsequent antineoplastic therapy or reintroduction of study treatment, whichever occurs earlier, unless otherwise specified. For MRD cohort, this is the overall period including pre-randomization phase and randomization phase. All by-arm summaries of the MRD cohort are also based on the overall period except DFS analyzed within randomization phase only. Summaries for CRR, ORR, MRD negativity rate within the pre-randomization phase (first 16 cycles) in the all treated population of MRD cohort will be provided as supportive analyses.

Table 2 summarizes the efficacy endpoints and analysis methods to be performed. For subgroup and exploratory or supportive analyses, only those providing meaningful information will be presented.

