**Table 2: Definitions and Analyses for Endpoints**

Endpoint	Definition	Analysis Method
Primary Endpoint for MRD Cohort (Not Applicable for FD cohort)		
1-year DFS rate in MRD-negative randomized subjects	DFS will be analyzed in MRD-negative randomized subjects and is defined as time from randomization date to MRD-positive relapse [1], or disease progression per investigator assessment or death from any cause, whichever occurred first. Subjects who do not experience any DFS event will be censored by the last MRD sample date with a valid result [2] or the date of last adequate disease assessment [3] after randomization, whichever occurs earlier. If no valid MRD result and no adequate disease assessment after randomization, DFS will be censored on the randomization date.	
Primary
 
The 1-year DFS rates will be estimated using Kaplan-Meier method and the corresponding 2-sided 95% CI will be provided. Z test for the difference of two proportions will be performed based on Kaplan-Meier estimates with standard error of each arm computed using Greenwood's formula.
 
Supportive
 
A log-rank test will be performed for between-arm comparison of DFS distribution. The hazard ratio and its 95% CI based on Cox regression model will be calculated. The 2-year DFS will be explored when median follow-up post randomization <math>\geq 2</math> years.

Endpoint	Definition	Analysis Method
Primary Endpoint for FD Cohort (Secondary Endpoint for MRD cohort)		

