MRD negativity rate	The proportion of subjects achieving MRD negativity which is defined as <1 CLL cell per 10,000 leukocytes (<1 x 10  ) as assessed by flow cytometry of a peripheral blood (PB) or bone marrow (BM) aspirate sample per central laboratory on or prior to initiation of subsequent antineoplastic therapy or, if applicable, reintroduction of study treatment, whichever occurs earlier.	
Primary The point estimate of MRD negativity rate and the corresponding 95% CI based on normal approximation to the binomial distribution will be provided.
 
Sensitivity MRD negativity rate by sample type (PB or BM)
 
Supportive MRD negativity rate by best overall response categories (CR/CRi, nPR/PR/PRL, and all others including non-responders and those off study without response assessment).

Tumor Lysis Syndrome (TLS) risk reduction	The reduction of the proportion of subjects who are at high risk of TLS after the ibrutinib lead-in compared with baseline.	
Primary The point estimate of the difference in proportions of subjects with high risk of TLS (at baseline - after ibrutinib lead in) and the corresponding 95% CI (adjusting correlation of paired data) will be provided.
 
Supportive Reduction of the proportion of subjects with hospitalization indicated due to tumor lysis Syndrome (TLS) risk (i.e. subjects with high TLS risk and subjects with medium risk of TLS and creatinine clearance <80 mL/min).

Progression Free Survival (PFS)	
Time from the date of first study treatment to the date of disease progression per investigator assessment or date of death from any cause, whichever occurs first, regardless of the use of subsequent antineoplastic therapy prior to documented PD or death.
 
For subjects without documented PD or death, PFS will be censored at the date of last adequate disease assessment. For subjects without adequate disease assessment post-baseline, PFS will be censored on the date of first study treatment.
	PFS distribution will be estimated by Kaplan-Meier method: median PFS and landmark estimates with 2-sided 95% CIs will be provided.

Overall Survival (OS)	Time from the date of first study treatment to the date of death from any cause. For subjects who are not known to have died at the time of the analysis, OS will be censored at the date of last known alive.	Kaplan-Meier estimates of median OS time and landmark estimates with 2-sided 95% CIs.

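### By-arm PFS and OS in the MRD cohort are timed from first dose, about 448 days before the arm is assigned, so their landmark rates and medians do not describe time on randomised treatment

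*SAP*

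**What the plan says.** Three statements in the SAP combine.

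- Section 4 sets the default clock: "the analysis period for primary analysis of endpoints is from the first dose date of study treatment". For the MRD cohort this overall period spans the pre-randomisation and randomisation phases.
- The same section applies it to the arms: "All by-arm summaries of the MRD cohort are also based on the overall period except DFS analyzed within randomization phase only".
- Table 2 defines PFS as "Time from the date of first study treatment to the date of disease progression per investigator assessment or date of death from any cause" and OS as "Time from the date of first study treatment to the date of death from any cause". For PFS, "median PFS and landmark estimates with 2-sided 95% CIs will be provided"; the OS row plans the same kind of output.

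The protocol uses the same origin. Section 10.4.6 reads "Progression-free survival (PFS) is defined as the time from the first dose date of study treatment until disease progression" and section 10.4.7 reads "Overall survival (OS) is defined as the time from the first dose date of study treatment until date of death due to any cause". Neither document gives a version of PFS or OS timed from randomisation.

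DFS is treated differently. In Table 2 it "is defined as time from randomization date to MRD-positive relapse", progression or death. The randomisation-based clock therefore already exists for one by-arm endpoint.

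**The concern.** An arm in this cohort exists only from Cycle 17. A subject who dies or has confirmed progression before then never joins one. Timing the arm's curve from Cycle 1 Day 1 credits it with event-free time that was a condition of entry (guarantee time).

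The cohort asks whether ibrutinib can be stopped after a confirmed MRD-negative response. A 24-month PFS rate in the placebo arm invites reading as two years off treatment, when most of that interval was spent on ibrutinib with or without venetoclax. The SAP also plans to explore 2-year DFS, counted from randomisation. A 2-year DFS rate and a 2-year by-arm PFS rate for the same arm would then share a label but run on clocks 1.23 years apart.

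The 24-month landmark is likely to be reported. The primary analysis waits until the last randomised subject could have had 1 year of randomised treatment, which is about 448 + 365 = 813 days after that subject's first dose.

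**Working it through.** **Plan's own figure.** The cohort's only stated design figure is about 80% power for 1-year DFS (60% vs 90%, 60 subjects randomised 1:1, two-sided 0.05). With 30 per arm and unpooled variance, the form closest to the planned z test, SE = √(0.6×0.4/30 + 0.9×0.1/30) and power is 81.6%, so it is reproduced (78.0% with pooled variance). It does not bear on this point. The documents give no PFS or OS rate for the randomised arms.

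**Step 1: lead time.**
- Inputs: pre-randomisation phase of 16 cycles (SAP 4); cycle of 28 days and randomised treatment from Cycle 17 Day 1 (SAP 1.1); randomisation at that visit or up to 3 days before (Protocol, Randomization Phase text following 8.2.1.7).
- 16 × 28 = 448 days; 448/365.25 = 1.23 years; 448/30.4375 = 14.7 months.
- If the visit and the randomisation each fall 3 days early: 442 days, or 1.21 years.

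**Step 2: can an event precede randomisation?**
- OS: no. A subject who has died cannot be randomised.
- PFS: almost never. MRD-negative subjects must be continuing ibrutinib and MRD-positive subjects both drugs (Protocol 5.1). Venetoclax may have stopped early only for a reason other than progression (3.1.1). Confirmed progression ends study treatment (7.3 and 9.2). No sentence lists absence of progression as a randomisation criterion, so a progression first seen before Cycle 17, confirmed later and back-dated, is a possible rare exception.

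**Step 3: what each landmark contains.**
- 12 months: 365 < 448, so nothing after randomisation. The OS rate is 100% whatever the arms do, and PFS is too apart from the exception above.
- 24 months: 730.5 − 448 = about 282 days (0.77 years), 39% of the interval.
- 36 months: 1095.75 − 448 = about 648 days (1.77 years), 59%.
- Median: with no event before day 448, the median from first dose is the post-randomisation median plus about 448 days.

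**Step 4: size, under an assumption.** Let S be the one-year post-randomisation event-free rate, with constant hazard after day 448 and no event before. The rate at t years is S^(t − 1.227) from first dose and S^t from randomisation. S is assumed.

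| Assumed S | 24 months: first dose / randomisation | Excess (points) | 36 months: first dose / randomisation | Excess (points) |
|---|---|---|---|---|
| 98% | 98.4% / 96.0% | 2.4 | 96.5% / 94.1% | 2.4 |
| 95% | 96.1% / 90.2% | 5.9 | 91.3% / 85.7% | 5.6 |
| 90% | 92.2% / 81.0% | 11.2 | 83.0% / 72.9% | 10.1 |
| 80% | 84.1% / 64.0% | 20.1 | 67.3% / 51.2% | 16.1 |
| 60% | 67.4% / 36.0% | 31.4 | 40.4% / 21.6% | 18.8 |

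The last row is a low extreme. The plan's 60% is a placebo DFS rate, which also counts MRD relapse, so it is not a PFS or OS assumption.

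**Step 5: the arm comparison.** Both arms of each randomisation carry nearly the same lead time, and the risk sets after day 448 are essentially those of a curve timed from randomisation. A hazard ratio would hardly change. Differences at a fixed landmark shrink: at assumed S of 80% and 90%, the 24-month difference is about 8 points from first dose and 17 from randomisation (81.0 − 64.0).

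**The case against.** The strongest case against is about scope and harm. No by-arm PFS or OS table is named. Protocol 10.4.6 and 10.4.7 place both endpoints in the all-treated population, where first dose is the proper origin, and the PFS and OS rows of SAP Table 2 mention no arms. SAP 4 limits supportive and exploratory analyses to those that are informative. SAP 1.6 makes everything except the primary endpoint descriptive. The holiday question is answered by DFS, which starts at randomisation and includes progression and death. A first-dose curve among randomised subjects also estimates exactly what its definition states, and the origin is given in both documents.

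Most of this stands as a limit on importance. It does not remove the point. The section 4 sentence covers every by-arm summary with DFS as the sole exception, so if by-arm PFS or OS is produced as written, it uses the first-dose clock.

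Three stronger readings are not supported:

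- A reader might infer that the arm comparison is biased. The lead time is nearly equal between arms, so its direction is not affected.
- A reader might infer that by-arm curves would look far better than the all-treated or FD curves. That depends on how many subjects fail before Cycle 17, and the documents give no such figure for this regimen. The nearest, 90% PFS at 18 months on single-agent ibrutinib (Protocol 1.4), does not suggest a large gap. The plan also describes no such comparison.
- A reader might infer that delayed entry (left truncation) at randomisation would repair a first-dose curve. Nearly everyone enters at about day 448, so the estimates after that day would be essentially unchanged.

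**Conclusion.** The point holds as one about absolute by-arm rates and medians. As written, by-arm PFS and OS in the MRD cohort start about 448 days before the arm exists. A 12-month rate is uninformative, and a 24-month rate reflects about nine months after randomisation. The event-free lead time is certain for OS; for PFS it is inferred from the on-treatment requirement and the discontinuation rule.

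The size of the excess rests on assumed event rates and a constant hazard. At 24 months it is about 2 points at 98%, 11 at 90% and 20 at 80%, so it is small if events are rare. The primary DFS test, the all-treated PFS and OS, and the direction of any arm contrast are untouched. The change is worth making because reported by-arm landmarks could mislead, but no confirmatory conclusion depends on it.

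**What to change.** - In SAP section 4 and Table 2, time by-arm PFS and OS in the MRD-negative and MRD-positive randomised populations from the randomisation date, as for DFS.
- Keep first dose as the origin for PFS and OS in the all-treated population.
- List the change in SAP section 6, because Protocol 10.4.6 and 10.4.7 use first dose. That section now records only a change of terminology.
- If first-dose by-arm curves are also shown, label them as conditional on reaching randomisation and give no landmark before about 15 months.

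The cost is a few lines of SAP text and one added derivation, using a date that DFS already requires. The by-arm landmark rates will look lower than they would from first dose.

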**Table 2: Definitions and Analyses for Endpoints**

Endpoint	Definition	Analysis Method
Primary Endpoint for MRD Cohort (Not Applicable for FD cohort)		
1-year DFS rate in MRD-negative randomized subjects	DFS will be analyzed in MRD-negative randomized subjects and is defined as time from randomization date to MRD-positive relapse [1], or disease progression per investigator assessment or death from any cause, whichever occurred first. Subjects who do not experience any DFS event will be censored by the last MRD sample date with a valid result [2] or the date of last adequate disease assessment [3] after randomization, whichever occurs earlier. If no valid MRD result and no adequate disease assessment after randomization, DFS will be censored on the randomization date.	
Primary
 
The 1-year DFS rates will be estimated using Kaplan-Meier method and the corresponding 2-sided 95% CI will be provided. Z test for the difference of two proportions will be performed based on Kaplan-Meier estimates with standard error of each arm computed using Greenwood's formula.
 
Supportive
 
A log-rank test will be performed for between-arm comparison of DFS distribution. The hazard ratio and its 95% CI based on Cox regression model will be calculated. The 2-year DFS will be explored when median follow-up post randomization <math>\geq 2</math> years.

Endpoint	Definition	Analysis Method
Primary Endpoint for FD Cohort (Secondary Endpoint for MRD cohort)		
Complete response rate (CRR)	The proportion of subjects achieving a best overall response of CR or CRi on or prior to initiation of subsequent antineoplastic therapy or, if applicable, reintroduction of study treatment, whichever occurs earlier.	
Primary The point estimate of CRR per investigator assessment and the corresponding 95% CI based on normal approximation to the binomial distribution will be provided. In FD cohort non-del17p population, p value for testing <math>CRR \leq 37\%</math> vs <math>CRR > 37\%</math> using asymptotic test for the binomial proportion will be calculated.
 
Sensitivity CRR per IRC assessment.
 
Supportive 1. Duration of complete response (DOCR defined as the interval between the date of initial CR or CRi until disease progression or death from any cause, whichever occurs first.) for subjects who achieved CR or CRi. 2. Durable CRR (defined as proportion of subjects with DOCR <math>\geq</math> 336 days (12 cycles))
 
Subgroup (defined in table 1) The point estimate of CRR per investigator assessment and its 95% CI by normal approximation to the binomial distribution for each subgroup.

Secondary Endpoints for MRD and FD Cohorts		
Overall response rate (ORR)	The proportion of subjects achieving a best overall response of CR, CRi, nPR, or PR on or prior to initiation of subsequent antineoplastic therapy or, if applicable, reintroduction of study treatment, whichever occurs earlier.	
Primary The point estimate of ORR per investigator assessment and the corresponding 95% CI based on normal approximation to the binomial distribution will be provided.
 
Sensitivity ORR per IRC assessment.

Duration of response (DOR)	Duration of response will be calculated for the subjects achieving a response (CR, CRi, nPR, PR) per investigator assessment and is defined as time from the date of initial response including PR with lymphocytosis to the date of disease progression or the date of death from any cause, whichever occurs first. For subjects without documented PD or death, DOR was censored at the date of last adequate disease assessment.	
Primary Kaplan-Meier estimates of median DOR time per investigator assessment and landmark estimates with 2-sided 95% CIs.
 
Sensitivity DOR per IRC assessment

Endpoint	Definition	Analysis Method
MRD negativity rate	The proportion of subjects achieving MRD negativity which is defined as <1 CLL cell per 10,000 leukocytes (<1 x 10  ) as assessed by flow cytometry of a peripheral blood (PB) or bone marrow (BM) aspirate sample per central laboratory on or prior to initiation of subsequent antineoplastic therapy or, if applicable, reintroduction of study treatment, whichever occurs earlier.	
Primary The point estimate of MRD negativity rate and the corresponding 95% CI based on normal approximation to the binomial distribution will be provided.
 
Sensitivity MRD negativity rate by sample type (PB or BM)
 
Supportive MRD negativity rate by best overall response categories (CR/CRi, nPR/PR/PRL, and all others including non-responders and those off study without response assessment).

Tumor Lysis Syndrome (TLS) risk reduction	The reduction of the proportion of subjects who are at high risk of TLS after the ibrutinib lead-in compared with baseline.	
Primary The point estimate of the difference in proportions of subjects with high risk of TLS (at baseline - after ibrutinib lead in) and the corresponding 95% CI (adjusting correlation of paired data) will be provided.
 
Supportive Reduction of the proportion of subjects with hospitalization indicated due to tumor lysis Syndrome (TLS) risk (i.e. subjects with high TLS risk and subjects with medium risk of TLS and creatinine clearance <80 mL/min).

Progression Free Survival (PFS)	
Time from the date of first study treatment to the date of disease progression per investigator assessment or date of death from any cause, whichever occurs first, regardless of the use of subsequent antineoplastic therapy prior to documented PD or death.
 
For subjects without documented PD or death, PFS will be censored at the date of last adequate disease assessment. For subjects without adequate disease assessment post-baseline, PFS will be censored on the date of first study treatment.
	PFS distribution will be estimated by Kaplan-Meier method: median PFS and landmark estimates with 2-sided 95% CIs will be provided.

Overall Survival (OS)	Time from the date of first study treatment to the date of death from any cause. For subjects who are not known to have died at the time of the analysis, OS will be censored at the date of last known alive.	Kaplan-Meier estimates of median OS time and landmark estimates with 2-sided 95% CIs.
Exploratory Endpoints for MRD and FD Cohorts		
		

[1] MRD-positive relapse is defined as an increase in CLL cells <math>\geq 1</math> per 100 leukocytes (<math>\geq 1 \times 10^{-2}</math>) confirmed on two consecutive occasions, after achieving MRD negativity, as assessed by flow cytometry of a PB or BM aspirate sample.
 
[2] MRD samples tested within 5 days after collection are considered valid and can be used in DFS analysis.
 
[3] Adequate disease assessment is defined as physical examination and CBC, or CBC and CT scan within 56 days of each other.
		

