ibrutinib significantly reduced the risk of progression or death by 84% compared to chlorambucil (median PFS not reached vs. 18.9 months respectively; hazard ratio, 0.16; $P < 0.001$). Notably, the 18-month PFS was 89% in both unmutated and mutated IGHV subgroups treated with ibrutinib, compared to 47% and 51% in these respective subgroups treated with chlorambucil. Additionally, ibrutinib reduced the relative risk of death by 84% (hazard ratio, 0.16; $P = 0.001$). The overall response rate was higher with ibrutinib compared with chlorambucil (86% vs. 35%, $P < 0.001$), and the rates of sustained increases from baseline values in the hemoglobin and platelet levels were higher with ibrutinib. Adverse events of any grade that occurred in at least 20% of the patients receiving ibrutinib included diarrhea, fatigue, cough, and nausea, and were mainly Grade 1-2. At 18.4 months of follow-up, 87% of the patients in the ibrutinib group continued on therapy (Burger 2015). Ibrutinib was approved by US FDA in March 2016 based on these data for the first line treatment of CLL.

Although ibrutinib has resulted in an improvement in PFS and OS in treatment-naïve patients (Burger 2015), and previously treated patients (Byrd 2014), single-agent ibrutinib has rarely demonstrated the ability to induce undetectable MRD by PCR or 4 color flow cytometry with a sensitivity of $< 1 \times 10^{-4}$. The addition of ibrutinib to bendamustine + rituximab (BR) resulted in a higher MRD-negative CR/CRi rate in previously treated CLL patients compared to placebo + BR (4.2% vs 1.5% by IRC; 9.3% vs 2.4% by investigator assessment) (Chanan-Khan 2016). The MRD-negative rate reached a plateau 9 months after completion of placebo + BR, however increased overtime with continued ibrutinib therapy (Fraser 2016).

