10.4. Efficacy Analysis

In general, the MRD cohort and the Fixed Duration cohort will be analyzed separately. Analysis details will be provided in the SAP.

Descriptive statistics and subject listings will be used to summarize the data. For continuous variables, the number of observations, means, standard deviations, medians, and ranges will be reported. For discrete variables, frequency will be summarized and the 95% confidence interval will be estimated. For time-to-event variables, Kaplan-Meier estimates will be provided. No inferential tests will be performed for pre-randomization phase. The primary endpoint, 1-year disease-free rate in MRD-negative randomized subjects, will be tested between placebo and ibrutinib arms at a 2-sided alpha level of 0.05. All the stratified analyses will be based on the randomization stratification factor, immunoglobulin heavy-chain variable region (IGHV) status.

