## 1.6. Testing Procedure and Level of Significance

For both cohorts, hypothesis testing will be performed independently (without multiplicity adjustment) for the primary endpoint only. Other endpoints will be summarized descriptively with 95% confidence interval (CI) whenever applicable.

- Primary endpoint for MRD cohort, 1-year DFS rate in MRD-negative randomized subjects, will be tested between placebo and ibrutinib arms at a 2-sided alpha level of 0.05.
- Primary endpoint for FD cohort, CRR, will be tested in non-del 17 subjects at a 1-sided alpha level of 0.025.

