### **1.7.2. Randomization Method**

After completing the 12 cycle Ibr + Ven treatment in MRD cohort, subjects will be randomized centrally by two separate schemes according to MRD status, each stratified by IGHV status (Unmutated vs mutated [including borderline or not evaluable]):

- Subjects who achieve confirmed MRD negativity are to be randomized to receive double blind study treatment, either placebo or ibrutinib.
- Subjects who do not achieve confirmed MRD negativity are to be randomized to receive open label treatment, either single agent ibrutinib or Ibr + Ven.

In each scheme, subjects will be randomized in a 1:1 ratio within each randomization stratum. This randomization scheme will be implemented within the IRT system.

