**Table 1: Baseline Subgroups**

Baseline Characteristics	Subgroups	Analysis Type
Age	<65 years, ≥65 years	• CRR
Gender	Male, Female	• MRD negativity rate
Race	White, Non-White	• Adverse Event
ECOG score	0, 1-2	• CRR • MRD negativity rate
Rai stage	Stage 0-II, III-IV	
Bulky disease	LDi <5 cm, ≥5 cm	
Del 17p	Yes, No	
Del 17p or TP53 mutated	Yes, No	
FISH*	Del 17p, Del 11q, Others	
IGHV per central lab	unmutated, mutated	
Creatinine clearance	<60 mL/min, ≥60 mL/min	• Adverse Event
NCI ODWG Liver Function Classification	Normal, Abnormal	

ECOG = Eastern Cooperative Oncology Group, FISH = Fluorescence in Situ Hybridization,  
NCI ODWG= National Cancer Institute Organ Dysfunction Working Group

\*Classified in 3 categories per hierarchical order (Dohner et al,2000): del 17p, del 11q without del 17p, and all others (neither del 17p nor del 11q identified).

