## **6. CHANGES IN PROTOCOL PLANNED ANALYSIS**

- The term “MRD-negative response” was replaced by the phrase “MRD negativity”.

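### SAP Table 2 names no strata for the supportive DFS log-rank test and Cox model; stratify both by the IGHV stratum used at randomization and leave the primary z-test as planned

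*SAP*

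**What the plan says.** SAP section 1.7.2 randomizes MRD-negative subjects 1:1 to ibrutinib or placebo within IGHV strata held in the IRT system. The coding is "Unmutated vs mutated [including borderline or not evaluable", so the last two categories sit with mutated. Protocol section 10.4 says "All the stratified analyses will be based on the randomization stratification factor", which it identifies as IGHV status. It does not list which analyses are to be stratified, and protocol section 10.4.2 leaves DFS details to the SAP.

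SAP Table 2 makes the primary DFS analysis a z-test on the Kaplan-Meier 1-year rates, with a Greenwood standard error for each arm. Two supportive comparisons follow: "A log-rank test will be performed for between-arm comparison of DFS distribution", and "The hazard ratio and its 95% CI based on Cox regression model will be calculated". Neither names strata or covariates. SAP section 1.6 states that "hypothesis testing will be performed independently (without multiplicity adjustment) for the primary endpoint only". SAP section 6, "CHANGES IN PROTOCOL PLANNED ANALYSIS", contains one terminology change and nothing about stratification.

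**The concern.** Allocation is balanced within IGHV strata by design. If IGHV also predicts DFS, that balance makes the log-rank numerator vary less between hypothetical trials than the unstratified variance formula assumes. The test then rejects less often than its nominal 5% under the null and gives up some power. A test stratified on the randomization factor uses the balance that the design creates.

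The two Cox models also answer slightly different questions. The unstratified model gives a marginal hazard ratio and the stratified model a within-stratum one. Apart from the primary z-test, these are the only between-arm DFS comparisons shown in Table 2, so they are the natural place for the stratified analyses that protocol 10.4 anticipates. What is at stake is the precision and interpretation of supporting evidence; the trial's formal conclusion does not depend on it.

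**Working it through.** **The plan's own figure.** SAP section 1.4 gives 60 randomized subjects, 60% versus 90% disease-free at 1 year, 2-sided 0.05, and about 80% power. With a separate variance per arm, as in the Greenwood z-test:

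SE = sqrt(0.6×0.4/30 + 0.9×0.1/30) = sqrt(0.011) = 0.1049; power = Φ(0.30/0.1049 − 1.96) = Φ(0.900) = 81.6%.

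The stated power reproduces, and the change proposed here does not touch it.

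**Inputs for the log-rank comparison**
- 30 per arm, placebo 60%, ibrutinib 90% (SAP 1.4). With no IGHV effect the implied hazard ratio is ln 0.9 / ln 0.6 = 0.206.
- Follow-up is 1 year for all, or uniform over 1-2 years. Both are assumptions; SAP 1.5.2 only sets the opportunity for 1 year of randomized treatment.
- Strata are 15/15 per arm, with 12/18 as a variant. Protocol 1.1.1 puts unmutated IGHV at about 40-50% of CLL; that this holds among MRD-negative subjects is assumed.
- The gap in placebo 1-year DFS between IGHV strata is not given in the documents, so it is varied over 0, 4, 18, 20 and 40 points around 60%. In protocol 1.1.2, 18-month PFS on ibrutinib is 89% in both subgroups (gap 0), "compared to 47% and 51% in these respective subgroups treated with chlorambucil" (gap 4). MRD negativity after chemoimmunotherapy is 33% versus 50.7% (gap about 18), but that is a different endpoint and setting. Gaps of 20 and 40 are an upper range without document support.

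**Method.** DFS is exponential in each stratum, with a common within-stratum hazard ratio set so that ibrutinib averages 90% (0.2063, 0.2061, 0.2027, 0.2018 and 0.1887 at the five gaps). The unstratified statistic is Z = Σ(observed − expected)/sqrt(ΣV) over all events. The stratified version computes both sums within each stratum and then adds them. There are 200,000 replicates per cell, so the standard error of a 5% rate is sqrt(0.05×0.95/200,000) = 0.05 points.

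| Follow-up | Gap | Null, unstratified | Null, stratified | Power, unstratified | Power, stratified | Change |
|---|---|---|---|---|---|---|
| 1 y | 0 | 5.07% | 5.06% | 80.08% | 79.98% | −0.1 |
| 1 y | 4 | 5.11% | 5.15% | 79.86% | 79.80% | −0.1 |
| 1 y | 18 | 4.64% | 5.09% | 80.24% | 80.83% | +0.6 |
| 1 y | 20 | 4.58% | 5.12% | 80.57% | 81.22% | +0.7 |
| 1 y | 40 | 3.15% | 5.15% | 81.53% | 84.62% | +3.1 |
| 1-2 y | 0 | 5.03% | 5.04% | 91.30% | 91.03% | −0.3 |
| 1-2 y | 4 | 5.08% | 5.08% | 91.19% | 90.94% | −0.3 |
| 1-2 y | 18 | 4.54% | 5.09% | 91.09% | 91.42% | +0.3 |
| 1-2 y | 20 | 4.48% | 5.20% | 91.27% | 91.69% | +0.4 |
| 1-2 y | 40 | 2.72% | 5.32% | 90.85% | 93.29% | +2.4 |

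Separately coded simulations with 100,000 replicates per cell agreed to within about 0.2 points, hence the rounded 4.5-4.8% for gaps of 18-20. The 12/18 split gives power changes close to these.

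**Hazard ratio.** Median Cox estimates (20,000 replicates) differ by at most 0.203 − 0.196 = 0.007 for gaps up to 20. At a gap of 40 they are 0.196 versus 0.180 (1 year) and 0.211 versus 0.184 (1-2 years), unstratified versus stratified.

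**Larger sample.** SAP 1.5.1 reports confirmed MRD negativity in 11 of 14 subjects. Projected to 150 enrolled, 150 × 11/14 = 117.9. At 58 per arm, power is 97.5% or more for both tests.

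**Primary test.** In 4,000 simulated trials per scenario, with IGHV hazard ratios of 1, 2 and 4, the unstratified z-test rejected in 3.2-5.3% under the null and had 82-84% power. There is no sign of inflation beyond simulation noise.

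**The case against.** The strongest reply is that nothing is wrong as it stands. A log-rank test and Cox model with no strata named are, on a natural reading, the plain two-arm versions, and they match a primary analysis that is itself unstratified and marginal. Stratifying only the supportive pair gives them a within-stratum target that the primary analysis does not have. At the documents' nearest PFS gaps (0 and 4 points), stratifying loses a little power and leaves the error rate alone; the visible gain comes only at an unsupported 40-point gap. The stratified test is not exactly nominal either: 5.2-5.3% at the larger gaps with 1-2 years of follow-up is small but beyond simulation error. SAP section 4 also lets the sponsor present only those supportive analyses that add meaningful information.

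Most of this stands. It keeps the point small and adds a second downside beside the lost power. It does not remove the case for analysing by the groups the trial randomizes by, at almost no cost.

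A reader might also infer that the SAP leaves the IGHV variable open, because Table 1 lists "IGHV per central lab" with only unmutated and mutated. The documents do not support that. Protocol 10.4 ties stratified analyses to the randomization factor, and SAP 1.7.2 defines its coding. The Table 1 variable is for subgroup summaries of complete response and MRD negativity rates, not for DFS.

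**Conclusion.** The point holds as a modest, optional improvement. As written, the two supportive DFS analyses would run without the factor on which subjects are randomized. Stratifying removes the conservatism that appears if IGHV predicts DFS: 0.3-0.7 points of power at an assumed 18-20 point gap, and 2.4-3.1 points at an assumed 40-point gap. Against that, it costs 0.1-0.3 points if IGHV has little or no effect, and null rejection can reach about 5.3% in small strata. These sizes rest on assumed IGHV gaps, exponential DFS, a common within-stratum hazard ratio and assumed follow-up; the documents give no IGHV effect on DFS after confirmed MRD negativity.

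Two stronger readings are tempting, and neither is supported. One is that the SAP breaches the protocol: section 10.4 names the factor for stratified analyses but does not require DFS to be stratified, so SAP section 6 had no departure to record. The other is that omitting strata inflates false positives or threatens the primary result. The unstratified log-rank test is nominal or conservative, it carries no alpha under SAP 1.6, and the primary z-test is fully specified and unaffected.

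**What to change.** In SAP Table 2, under Supportive for 1-year DFS, state that the log-rank test and the Cox model are both stratified by the IGHV stratum recorded in IRT at randomization (unmutated versus mutated, with borderline or not evaluable counted as mutated). Add that the Cox hazard ratio is a within-stratum estimate. Leave the Kaplan-Meier/Greenwood z-test as the primary analysis, unchanged, and add no stratified version of it.

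The cost is one or two sentences and a strata term in two planned analyses. No new data are needed, since every randomized subject already has an IRT stratum. The wording should be settled before the treatment assignments are unblinded for analysis.
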